4. SYNOPSIS

Trial Title	STENT RETRIEVER THROMBECTOMY FOR THROMBUS BURDEN REDUCTION IN PATIENTS WITH ACUTE MYOCARDIAL INFARCTION		
Internal ref. no. (or short title)	RETRIEVE – AMI study		
Trial registration	NCT05307965		
Sponsor	Oxford University Hospitals NHS Foundation Trust		
Funder	Medtronic & Terumo Inc		
Clinical Phase	Device Pilot		
Trial Design	Randomised controlled trial		
Trial Participants	ST elevation Myocardial Infarction Patients		
Sample Size	n=81		
Planned Trial Period	Start Date: 01/03/2022 End Date: 30/09/2025		
Planned Recruitment period	36 months		
	Objectives	Outcome Measures	Timepoint(s)
Primary	Efficacy of thrombus burden reduction	Thrombus volume (mm ³) (OCT assessment)	Pre-stent
Co-primary	Safety of retriever thrombectomy	• Angiography-/OCT-defined device related target vessel complications, device deficiency	Pre-stent
		• Rate of major adverse cardiac and cerebrovascular events (MACCE)	In hospital 30 days 6 months
Secondary	Efficacy of thrombus burden reduction	Thrombus area, flow area (mm ²) (OCT assessment)	Pre-stent
	Efficacy of thromboatheroma reduction	Thromboatheroma area, flow area (mm ²) (OCT assessment)	Post-stent
	Efficacy of stent implantation	Stent expansion & apposition (OCT assessment)	Post-stent
	Angiographic success rate	TIMI flow, Myocardial Blush Grade, Angiography derived coronary physiology indices	Post-stent
Intervention(s) • Other intervention(s)	Percutaneous coronary intervention with adjunctive use of stent retriever thrombectomy		
Comparator	Percutaneous Coronary Intervention alone or Percutaneous coronary intervention with adjunctive aspiration thrombectomy		

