8. OBJECTIVES AND OUTCOME MEASURES

Objectives	Outcome Measures	Timepoint(s) of evaluation of this outcome measure (if applicable)
Primary Objectives		
Efficacy of thrombus burden reduction	Thrombus volume (mm ³) (OCT assessment)	Pre-stent
Safety of retriever thrombectomy	
Angiography-/OCT-defined device related target vessel complications, device deficiencyRate of major adverse cardiac and cerebrovascular events (MACCE)	Pre-stent In hospital 30 days 6 months
Secondary Objectives		
Efficacy of thrombus burden reduction	Thrombus area, flow area (mm ²) (OCT assessment)	Pre-stent
Efficacy of thromboatheroma reduction	Thromboatheroma area, flow area (mm ²) (OCT assessment)	Post-stent
Efficacy of stent implantation	Stent expansion & apposition (OCT assessment)	Post-stent
Angiographic success rate	TIMI flow, Myocardial Blush Grade, Angiography derived coronary physiology indices	Post-stent

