11.5. Blinding and code-breaking

Due to the interventional nature of the trial, masking and code-breaking procedures are not applicable.

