13. SAFETY REPORTING

13.1. Definitions

Adverse Event (AE)	Any untoward medical occurrence, unintended disease or injury or any untoward clinical signs (including an abnormal laboratory findings) in participants, users or other persons whether or not related to the investigational medical device. This includes events related to the investigational device or comparator, events related to the procedures involved (any procedure in the protocol). For users or other persons this is restricted to events related to the investigational medical device.
Adverse Device Effect (ADE)	An adverse event related to the use of an investigational medical device. This definition includes any events resulting from insufficient or inadequate instructions for use, deployment, implantation, installation, or operation, or any malfunction of the investigational device. This definition also includes any event resulting from user error or form intentional misuse of the investigational device.
Serious Adverse Event (SAE)	Any untoward medical occurrence that: 
• Results in death• Is life-threatening,• Requires inpatient hospitalisation or prolongation of existing hospitalisation,• Results in persistent or significant disability/incapacity, or• Is a congenital anomaly/birth defect.• Other important medical events.

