13.2. Causality

The relationship of each adverse event to the trial device may be determined by the manufacturer and/or a medically qualified Investigator according to the following definitions:

Not related: The event is clearly related to other factors such as the patients/participants clinical condition, therapeutic intervention, concomitant medication.

Unlikely: The event is probably produced by other factors such as the patients/participants clinical condition, therapeutic intervention, concomitant medication and does not follow a known response pattern to the device

Possibly: The event follows a reasonable temporal relationship from the time of placement/administration and/or follows a known response pattern to the device but could have been caused by other factors such as the patients/participants clinical condition, therapeutic intervention, concomitant medication.

Most probable: The event follows a reasonable temporal relationship from the time of placement/administration and/or follows a known response pattern to the device and could not have been caused by other factors such as the patients/participants clinical condition, therapeutic intervention, concomitant medication. Further the event immediately follows the administration/placement of the device and improves on stopping or removing the device.

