14.2. Analysis of Endpoints

In keeping with our usual practice, we will obtain expert statistical advice from the Centre for Statistics in Medicine (or equivalent) for each specific task. A flow diagram detailing number of participants screened and randomised will be provided. Analysis of the OCT-derived primary and secondary endpoints (including angiography-derived) will be conducted offline in a blinded fashion. Summary statistics, including means, medians, and variances, will be calculated at each time point and for each type of data and group (e.g. baseline characteristics, parameters derived from OCT, angiography-derived coronary physiology). The distribution of the levels will be described. For each parameter an analysis of variance will be carried out.

An analysis evaluating for a between group difference in pre-stent thrombus volume will first use an 1-way ANOVA with a 2-sided equality test to assess for an overall trend. Post-hoc analyses exploring the following hypotheses i) retriever thrombectomy (Arm 3) is different to no thrombus modification (arm 1) and ii) retriever thrombectomy (Arm 3) is different to aspiration thrombectomy (Arm 2) will be performed using the Dunnett test. Control of the Type I error at 5% two-sided significance level due to multiple testing will be achieved using Dunnett's method.³⁶ Missing data for the primary analysis will be dealt with complete case analysis if data missingness is <10% (<3 cases per group). If missingness is higher, multiple imputation will be performed instead. Major adverse cardiac and cerebrovascular events will be analysed using proportions statistical testing (Fisher's exact or χ^2 tests), yet they represent an exploratory analysis.

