14.3. Interim Safety Analysis

Based on the reported coronary perforation (0.37%), coronary dissection (7.7%) and transient ischaemic attack/ischaemic stroke (0.25-0.8%) rates in contemporary STEMI practice, in a 27-patient arm study, 1 coronary perforation, 1 significant coronary dissection and 1 transient ischaemic attack/ischaemic stroke may be expected by chance. If >2 (>10%) coronary perforation-related SADEs or >2 significant coronary dissection-related SADEs or >2 transient ischaemic attack-/ischaemic stroke-related SADEs occur in the investigational device arm this will be considered too high.

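### The co-primary vessel-injury endpoint counts only device-related complications, so it rests on unmasked attribution and leaves out the randomised background rate

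*Combined protocol and SAP*

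**What the plan says.** Under the objective "Safety of retriever thrombectomy", Sections 4 and 8 list two co-primary measures: MACCE, and "Angiography-/OCT-defined device related target vessel complications, device deficiency". The second is assessed pre-stent.

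Section 14.2 provides for blinded reading: "Analysis of the OCT-derived primary and secondary endpoints (including angiography-derived) will be conducted offline in a blinded fashion". Treatment itself is open; Section 11.5 states that "masking and code-breaking procedures are not applicable".

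Relatedness is dealt with elsewhere. Section 13.2 says: "The relationship of each adverse event to the trial device may be determined by the manufacturer and/or a medically qualified Investigator". The manufacturer is also listed as a funder in the synopsis. Section 13.1 defines an adverse device effect as "An adverse event related to the use of an investigational medical device", but says of adverse events in general: "This includes events related to the investigational device or comparator". The endpoint itself does not define the word device.

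Section 11.6 has every arm wired, predilated with a 1.5 mm balloon and imaged by OCT before stenting. Arm 1 then has no thrombus modification, and its baseline OCT serves as its pre-stent measurement. Section 13.1 grades dissections and perforations by the NHLBI and Ellis schemes, and Section 13.3 records all adverse events whatever their attribution. Section 14.2 names no analysis suited to a binary complication endpoint; its Fisher and chi-squared tests are for MACCE.

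**The concern.** A complication enters this endpoint in two steps. Someone must see the injury, and someone must decide that the device caused it. The first step can be blinded. The second cannot be done for the retriever by a reader who does not know whether one was used, so it falls to people who know the arm. The plan does not connect the two steps.

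The restriction also removes the purpose of randomised controls for this outcome. The wire, balloon and OCT catheter can each injure the vessel in any arm, and Section 13.9 accepts that any intracoronary device can cause local complications. An Arm 1 patient with such an injury does not count, because no thrombectomy device was used. An Arm 3 patient with the same injury may count, depending on who attributes it.

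This is the main vessel-injury result for a device used off-licence in coronary arteries. The error can run either way. Generous attribution to the wire or balloon hides an excess; strict attribution to the retriever against controls fixed at zero creates one.

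**Working it through.** The plan gives no expected figure, test or margin for this endpoint, so there is none to reproduce. The check shows what the definition does to a comparison that a reader would naturally make.

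**Inputs**
- 27 patients per arm (Section 14.1), so 54 in Arms 1 and 2 together.
- Background pre-stent injury rate: not in the documents. I assume 3% to 7.7%. The upper value is borrowed from the dissection rate in Section 14.3. Section 12.2 shows that it is an edge-dissection rate after stenting, so it is only a stand-in. The one significant dissection per arm in Section 14.3 corresponds to 1/27 = 3.7%, inside this range.
- Fisher's exact test, two-sided, Arm 3 against pooled controls. The plan specifies neither this test nor this pooling for the endpoint.

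**Step 1: controls zero by definition.** Suppose three Arm 3 injuries are counted: 3/27 against 0/54. Given three events in 81 patients, the chance that all fall in Arm 3 is C(27,3)/C(81,3) = 2,925/85,320 = 0.034. The opposite extreme (none in Arm 3) has probability 0.29, so the two-sided p is 0.034. For 2/27 against 0/54, p = 0.108.

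**Step 2: controls counted in the same way.** At 7.7%, 54 × 0.077 = 4.2 control events are expected; take 4. Given seven events in 81, the only split more likely than 3 in Arm 3 is 2 in Arm 3, with probability 0.319. So p = 1 − 0.319 = 0.68.

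Sensitivity to the control count, with Arm 3 fixed at 3/27:

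| Controls (of 54) | 0 | 1 | 2 | 3 | 4 |
|---|---|---|---|---|---|
| Fisher p | 0.034 | 0.11 | 0.33 | 0.39 | 0.68 |

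Exact 95% intervals: 3/27, 2.4% to 29.2%; 0/54, 0% to 6.6%; 4/54, 2.1% to 17.9%.

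**Step 3: how often a spurious difference would appear.** Suppose the retriever adds no injury. With controls fixed at zero, Step 1 shows that p < 0.05 needs at least 3 counted events in Arm 3, so the rate is P(X ≥ 3) for a binomial with n = 27. (This 3 comes from Fisher's test, not from the stopping rule.)

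| True rate, all arms | Controls zero, all Arm 3 injuries counted | Controls zero, half counted | All arms counted alike |
|---|---|---|---|
| 3% | 4.6% | 0.8% | 1.2% |
| 5% | 15% | 2.9% | 2.1% |
| 7.7% | 34.5% | 8.4% | 2.8% |

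The two middle columns differ only in attribution.

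**Step 4: limits of the illustration.** Against a single control arm, 3/27 against 0/27 gives p = 0.24, and the spurious rate is at most 1.5% over the same range. The change in apparent significance therefore appears only with pooled controls.

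**Step 5: what a like-for-like count can detect.** With all arms counted alike and controls at 7.7%, power for 27 against 54 is 14.5% if the Arm 3 rate is 15%, and 30% if it is 20%.

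**The case against.** A reader might infer that the device-related restriction and the blinded reading contradict each other. They do not. Section 14.2 does not ask blinded readers to judge relatedness, and Section 13.2 assigns that to others. Blinded detection followed by separate attribution satisfies both; what is missing is the link between them.

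It is also tempting to say that both control arms are fixed at zero. That is firm for Arm 1 only. Arm 2 receives an aspiration catheter, and its events could count on a wider reading of device.

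Nor are the background data lost. All adverse events are recorded, injuries are graded without attribution, and every arm has a pre-stent OCT. In Arms 2 and 3 the wire and balloon steps precede the Stage 2 OCT and the thrombectomy device follows it. An injury absent at Stage 2 and present at Stage 3 therefore arose after those steps. The plan does not state this use, but the images allow it.

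A reader might think the endpoint is judged against the rates that open Section 14.3 ("Based on the reported coronary perforation (0.37%), coronary dissection (7.7%) and transient ischaemic attack/ischaemic stroke (0.25-0.8%) rates in contemporary STEMI practice"), or against its limit of more than two events. Both serve the rule for halting on serious adverse device effects, and nothing applies them to this endpoint.

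Finally, this is an exploratory pilot whose stated objective is retriever safety. No between-arm test of this endpoint is promised, and MACCE, the other co-primary safety measure, is not restricted by attribution. These points stand and limit the weight of the concern. They do not supply an all-arm injury rate, which no section plans.

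**Conclusion.** The concern holds as a weakness of definition and analysis, not of data capture. As written, the main vessel-injury result depends on attribution by unmasked parties. It scores Arm 1 zero by construction, and Arm 2 as well if device means the retriever.

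The size depends on assumptions. With three counted events in Arm 3, p moves from 0.034 to 0.68 if controls go from zero by definition to 4/54. That assumes pooled controls, a test not specified for this endpoint, and a background near 7.7% taken from a post-stent rate. At a 3% background, or against one control arm, the distortion of a formal test is small. The dependence on who attributes, and the missing background rate, remain in every case.

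The documents do not support the stronger conclusions that the plan's rules are incompatible or that control injuries go unrecorded. This is a cheap improvement worth making.

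**What to change.** In Sections 4, 8 and 14.2:

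1. Define the outcome as all target-vessel complications defined by angiography or OCT and present at the last pre-stent assessment, in all three arms, irrespective of attributed cause. That assessment is Stage 2 for Arm 1 and Stage 3 for Arms 2 and 3.
2. Have the blinded offline reading already planned grade them by the NHLBI and Ellis schemes in Section 13.1.
3. Report each arm's count, denominator and exact 95% confidence interval, and call the comparison descriptive.
4. Keep the attributed subset and device deficiency as a secondary listing for Arms 2 and 3. State what device covers and who attributes. The Stage 2 and Stage 3 OCT pair can help separate injuries that arose after the wire and balloon steps.

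The cost is wording; the events, grading and imaging are already planned. The reported rate will include background events and so be somewhat higher. Arm 1 has one pre-stent OCT pass where Arms 2 and 3 have two, so its background rate covers slightly less instrumentation; say so in the report. The comparison has low power (Step 5) and should not be presented as showing equal safety. The halting rule in Sections 13.6 and 14.3 is not affected.

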5. ABBREVIATIONS

AE	Adverse event
ADE	Adverse device effect
CI	Chief Investigator
CRF	Case Report Form
CTA	Clinical Trials Authorisation
CTRG	Clinical Trials and Research Governance
GCP	Good Clinical Practice
GP	General Practitioner
HRA	Health Research Authority
ICH	International Conference on Harmonisation
IRB	Independent Review Board
MACCE	Major adverse cardiac and cerebrovascular event
MHRA	Medicines and Healthcare products Regulatory Agency
NHS	National Health Service
RES	Research Ethics Service
OCT	Optical coherence tomography
OXTREC	Oxford Tropical Research Ethics Committee
PCI	Percutaneous coronary intervention
pPCI	Primary percutaneous coronary intervention
PI	Principal Investigator
PIL	Participant/ Patient Information Leaflet
R&D	NHS Trust R&D Department
REC	Research Ethics Committee
RMP	Registered Medical Practitioner
SAE	Serious Adverse Event
SADE	Serious Adverse Defice Effect
SOP	Standard Operating Procedure
TIMI	Thrombolysis in myocardial infarction
TMF	Trial Master File
TSG	Oxford University Hospitals NHS Foundation Trust Trials Safety Group

6. BACKGROUND AND RATIONALE

Ischaemic heart disease remains the leading cause of death across the globe despite sustained reductions in mortality rates.¹ However, cardiovascular morbidity following myocardial infarction remains a significant burden to healthcare systems. Our attempts during the last decade have thus shifted towards reperfusion therapies that reduce the extent of the myocardial infarction.²

Amongst the proposed adjuncts to angioplasty, aspiration thrombectomy has been proposed as a simple method of removing the in-situ clot prior to stent deployment. Aspiration thrombectomy was thought to reduce distal embolisation of athero/thrombotic debris, limiting the ensuing microvascular dysfunction and final infarct size.^{3,4} Early randomised controlled trials of aspiration thrombectomy supported its routine clinical use,⁵ but contemporary trials suggest no effect on mortality and a signal of increased stroke.^{6,7} Amongst the reasons put forward to explain the lack of benefit of aspiration thrombectomy is its inefficacy in removing thrombi.⁸ Indeed, the optical coherence tomography (OCT) sub-study of TOTAL suggested that there was no difference in pre-PCI thrombus volume in lesions treated with aspiration thrombectomy versus PCI alone.⁹

One of the reasons why thrombus-aspiration catheters failed to remove thrombotic debris in STEMI can be related to the inability of the devices to actually interact with the clot. In the coronary artery the clot develops on top of an ulcerated/ruptured plaque, meaning that the bulk of the clot is often in an eccentric position, eventually protruding towards the centre of the lumen. An additional element that must be taken into account is the disproportion between the vessel lumen-cross-section-area (which can potentially be filled with thrombus) and the aspiration-opening area at tip of the aspiration catheter. If an average size coronary artery (diameter: 3.0 – 3.5 mm) is considered, the vessel lumen-cross-section-area can range from 7.06 to 9.61 mm². Since the aspiration-opening area at tip of the aspiration catheter is on average 0.9-1.0 mm², that means that the thrombectomy device technically covers (on average) from 9.4 to 14.2% of the vessel lumen-cross-section-area. In a larger caliber vessel (for example large ectatic right coronary arteries) this ratio becomes even more unfavourable. As the caliber of the vessel increases, its “theoretical” ability to contain large thrombus-burden increases proportionally, meaning that

Clinical Trial Protocol Template version 15.0
CONFIDENTIAL

© Copyright: The University of Oxford and Oxford University Hospitals NHS Foundation Trust 2019

Page 10 of 57

paradoxically the currently available aspiration devices become less effective in those cases when they would be required to work at their best.

Another element to account for poor performance of the current aspiration-catheters is the “guidewire bias effect”. This is a direct consequence of 1) the coronary arteries not being straight tubes, but having bends and curves and 2) of the thrombectomy-catheter sliding over an angioplasty-guidewire during the procedure. In a curved tube, like the coronary artery, the position of the wire can actually bias the aspiration device away from the clot. The “guidewire bias effect” can be minimally influenced by the operator. For this reason a clot-removal device that could interact with the whole vessel-lumen cross section area (and thus with the whole clot) and whose mode action is not affected by coronary artery caliber and by “guidewire bias effect” would be desirable and likely to be more effective in removing thrombus in STEMI patients.

Stent-retriever thrombectomy technology has this property and not surprisingly it has revolutionised the treatment of acute ischaemic stroke improving recanalization rates and clinical outcomes significantly.^{10,11} Stent-retriever technology has been proved to be safe with low rates of vascular perforations (~2.1%) and iatrogenic dissection (1.7%-3.5%) in acute ischaemic stroke treatment.¹⁰⁻¹⁴

Isolated case reports of successful bailout stent-retriever thrombectomy in ST elevation myocardial infarction (STEMI) patients attest to the feasibility of a stent-retriever thrombectomy approach in STEMI.^{15,16} However whether a stent-retriever strategy is more effective than conventional thrombus aspiration in STEMI has to be proved. Recently, stent retriever thrombectomy with the NeVa (Vesalio) device was evaluated in STEMI patients with large thrombus burden.¹⁷

We set out to study the efficacy and safety of retriever thrombectomy in a carefully selected cohort of patients with ST elevation myocardial infarction and compare it with current standard of care; standalone PCI or PCI with adjunctive thrombus aspiration. We expect that stent retriever thrombectomy will more effectively reduce the thrombotic burden when compared to the current standard of care (e.g. standalone PCI and/or PCI with adjunctive aspiration thrombectomy).

7. HYPOTHESIS

We hypothesize that stent retriever thrombectomy will be more efficacious than aspiration or mechanical thrombectomy in thrombus burden reduction as assessed by OCT derived pre-stent thrombus volume (mm³).

8. OBJECTIVES AND OUTCOME MEASURES

Objectives	Outcome Measures	Timepoint(s) of evaluation of this outcome measure (if applicable)
Primary Objectives		
Efficacy of thrombus burden reduction	Thrombus volume (mm ³) (OCT assessment)	Pre-stent
Safety of retriever thrombectomy	
Angiography-/OCT-defined device related target vessel complications, device deficiencyRate of major adverse cardiac and cerebrovascular events (MACCE)	Pre-stent In hospital 30 days 6 months
Secondary Objectives		
Efficacy of thrombus burden reduction	Thrombus area, flow area (mm ²) (OCT assessment)	Pre-stent
Efficacy of thromboatheroma reduction	Thromboatheroma area, flow area (mm ²) (OCT assessment)	Post-stent
Efficacy of stent implantation	Stent expansion & apposition (OCT assessment)	Post-stent
Angiographic success rate	TIMI flow, Myocardial Blush Grade, Angiography derived coronary physiology indices	Post-stent

